Genetic and epigenetic features of tumour and immune cells	x x																	x x
Body composition																		
Wellbeing indices	Х																	Х
Heart rate and blood pressure	х																	х
Physical fitness	х																	Х
Control measures																		
Dietary intake	Х																	Х
Physical activity level	Х		Х				Х				Х				Х			Х
General health status	х																	х

Background and Summary

Chronic lymphocytic leukaemia (CLL) is the most common adult leukaemia in the UK with an estimated annual incidence of 7.6 per 100,000 people (Smith et al., 2018).

CLL is characterised by the clonal proliferation and accumulation of mature B cells within the blood, bone marrow, lymph nodes and spleen (Hallek et al., 2018a). The most common presentation of CLL is the incidental discovery of a B cell lymphocytosis, of at least 5000 B cells per μ L of peripheral blood, sustained for at least 3 months (Hallek et al., 2018a). Diagnosis is subsequently confirmed by evaluating the blood smear, B cell clonality and immunophenotype.

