In addition to establishing the benefits of exercise training in people with 'watch and wait' CLL, this study provides a unique methodological model to investigate the effects of exercise on neoplastic activity in humans. Given that CLL tumour cells are highly abundant in peripheral blood (>5000 cells/ul) and thus easily and relatively non-invasively accessible, and the absence of confounding therapies (e.g. anti-cancer therapy), that are typical of other cancer diagnoses, people with 'watch and wait' CLL provide a unique model to prospectively assess the short-term effects of exercise training on tumour cell mass and activity *in vivo*, and in doing so conduct mechanistic investigations to discover how regular exercise averts tumour growth in humans. A number of anti-tumour mechanisms of exercise have been proposed, including immune function, inflammation, adipose tissue and metabolic hormones (McTiernan, 2008), which will be explored as secondary outcome measures in our study herein.

Accordingly, this study aims to confirm the safety and acceptability of an exercise programme in people with 'watch and wait' CLL, as well as preliminarily explore the effects of exercise training (pre-intervention to post-intervention) on tumour cell mass (CLL tumour cell frequency) in peripheral blood. The aforementioned data will be used as preliminary data for a power calculation, for a future larger randomised control trial. Additionally, this study will enable preliminary assessment of changes (pre-intervention to post-intervention) to a wide range of health outcomes in people with 'watch and wait' CLL, including cardiorespiratory fitness, strength, body composition, free-living physical activity levels, and wellbeing and physical function indices. Finally, this study will enable preliminary assessment of the changes (pre-intervention to post-intervention) to the potential anti-tumour mechanisms of exercise including immune function, inflammation, adipose tissue and metabolic hormones.

The hypotheses of this pilot study are as follows:

- Exercise will be safe and acceptable in people with 'watch and wait' CLL.
- Exercise will reduce the frequency of CLL tumour cells in the peripheral blood of people with 'watch and wait' CLL.
- Exercise will improve the cardiorespiratory fitness and the health and wellbeing of people with 'watch and wait' CLL.

Aims and outcomes

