The present trial will investigate the safety and acceptability of a 16-week home-based, progressive, exercise training intervention.

Primary objective:

1. Investigate the safety and acceptability of an exercise training intervention, in physically inactive people, with 'watch and wait' CLL.

Outcome measures, collected throughout the trial period:

- Safety (incidence and severity of adverse events)
- Uptake (proportion of people approached who attend screening, proportion of people who attend screening that are deemed eligible)
- Adherence (proportion of exercise sessions prescribed that are actually completed)
- Compliance (prescribed vs. actual aerobic exercise performed per exercise session)
- Retention (the proportion of participants who complete baseline measures that also complete follow-up measures)

Secondary objective:

1. Investigate the effect of an exercise training intervention on CLL disease activity, immune markers, overall fitness, health and wellbeing in physically inactive people, with 'watch and wait' CLL.

Outcome measures, collected pre- and post-trial period:

- Frequency of CLL cells in peripheral blood measured by flow cytometry
- Immune competency (e.g. phenotypic and functional analyses of PBMCs, differential blood count, viral infection history, immunoglobulins, complement proteins)
- Basal inflammation (e.g. cytokines)
- Metabolic factors and hormone levels (e.g. glucose, insulin, growth factors)
- Clonality of tumour cells (e.g., PCR).
- Genetic and epigenetic features of tumour and immune cells.
- Cardiorespiratory fitness (predicted, or VO_{2MAX})
- Body strength (measured by 1-rep max resistance exercises)
- Body composition (height, weight, waist and hip circumference, fat mass, lean mass)
- Wellbeing indices (stress, fatigue, sleep, quality of life, frailty, motivation, self-efficacy)
- Free-living physical activity levels via wearable technology (e.g., duration, intensity, frequency, energy expenditure and sedentary time)
- Physical function (e.g., flexibility, sit-to-stand test)
- Resting blood pressure, and heart rate
- Left ventricular (LV) function (volumes; ejection fraction; strain; diastolic function)
- Comparison of LV manual measures with artificial intelligence

Trial design

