The participant will be given resources and equipment (i.e., an instruction pack, food diary and activity monitor) for these measures at Visit 1 after informed consent has been obtained. This allows measures to be completed prior to Visit 2 which will be scheduled a minimum of 9 days after screening.

Dietary composition: Participants will be provided with a 3-day food diary and instructions that explain how best to record everything they eat (e.g. cooking method, brand) for two weekdays and one weekend day. The records will be analysed using Nutritics software with the primary aim of characterising any changes to dietary intake between measurement points.

Physical activity: Participants will be given a GENEActiv physical activity monitor at six measurement points throughout the study, initially at Visit 1 to enable measures of free living physical activity level to be taken prior to Visit 2 (pre trial period), a further four times during the trial period (weeks 2, 6, 10 and 14), to enable measures of free living physical activity level to be taken throughout, and a final time (post trial period) to enable measures to be taken after the trial (post trial period) has been completed. At each measurement point the participants will be asked to wear the monitor for 9 days (to capture at least 7 full days of wear) for measurement of free-living physical activity. The monitor is worn on the wrist and records acceleration and skin temperature continuously. No identifiable data is collected by the GENEActiv. Participants will be provided with instructions on how to use the monitor and these

instructions emphasise the importance of wearing the monitor continuously, the monitor is waterproof so can be worn during waterborne activities (e.g. showering/swimming). Data from complete days (>80% wear time) will be reported to examine any change in physical activity level between measurement points. The GENEActiv physical activity monitor will be loaned to the participant for the duration of measurement only. The devices are covered by the University of Bath insurance policy.

Visit 2 (Week 0)

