A final important consideration for the research team when designing this study was the global COVID-19 pandemic. To minimise this risk, the exercise training intervention has been designed to be conducted in participants homes. Appropriate personal protective equipment (PPE) will be worn by the research team during Visit 1, Visit 2 and Visit 3 and the study will adopt the policies that the Trust is following and will begin recruiting when the host institution allows it.

COVID-19 Mitigation Strategies

Given safety and institutional directives with the COVID-19 pandemic in the UK, the research team will adhere to the below policies and procedures:

• Any team member displaying any COVID-19 symptoms (fever (38°C or higher), or sense of having a fever, cough, shortness of breath, muscle aches, sore throat, unexplained loss of taste or smell, diarrhoea, headache) must stay at home and organise for a COVID-19 test by contacting their GP.

- Participants and research team will use hand sanitiser on entry to the University
- The research team will be provided with appropriate PPE (apron, gloves and a face covering/face mask and face shield throughout study participant visits)
- The research team will change gloves and apron between every study participant contact
- The research team will thoroughly wash hands and forearms before and after the session (not just use hand sanitiser)
- All research equipment will be wiped down immediately with disinfectant spray and cloth between study participant sessions
- Where possible staff will be vaccinated, and lateral flow tests will be done.
- Only two members of the research team will enter the participants homes to deliver the exercise equipment, and they will be in the home for no more than 15 minutes.

Statistics and data analysis

Sample size

The aim is to recruit 40 participants. Assuming a recruitment rate of three to four people per month and 20% drop out, we estimate the target can be reached within a suitable time-frame of the funding period (16-18 months).

There is limited information available to enable a formal sample size calculation. This pilot trial will provide preliminary data to determine that a future RCT has promise and is not futile, and to perform a sample size calculation.

Statistical analysis plan

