Primary outcome measures do not lend themselves to statistical analysis. Safety will be reported as the incidence and severity of adverse events. Acceptability will be reported as proportions in terms of uptake, adherence, compliance and retention.

Secondary data will be tested for normality (e.g. Shapiro-Wilk) and in the event that some data are not normally distributed, the data will be log transformed. Descriptive statistics will be presented, and longitudinal differences and interaction effects will be identified using repeated-measures T-tests. These data will be used to inform sample size calculations in a future RCT. Incomplete data and missing values will be managed using an intention-to-treat approach with multiple imputation.

The project may utilise correlation analysis to establish whether any change in disease activity is associated to a number of mechanistic markers, and stepwise multiple regression will identify the extent to which a change in the mechanistic markers predict change in disease activity. Subgroup analysis may be performed, e.g. split to high vs. low responders or by presence of mediating variable(s) for further analysis.

Monitoring, audit and inspection

The University of Bath, as Sponsor, will monitor and conduct random audits on a selection of studies in its clinical research portfolio. Monitoring and auditing will be conducted in accordance with the Department of Health Research Governance Framework for Health & Social Care (April, 2005), and in accordance with the Sponsor's monitoring and audit policies and procedures.

Patient safety will be monitored on an ongoing basis by the research and healthcare team. A formal data monitoring committee will not be convened as this is a small single-centre pilot study. Instead, the research team will present an update on safety at quarterly trial management group meetings, together with the haematologist ([name] and/or [name]), the CI ([name]), and patient representative(s).

Ethical and regulatory considerations

Research Ethics Committee (REC) review

Before the start of the trial, approval will be sought from an NHS REC for the trial protocol, informed consent forms, participant information sheet and recruitment letter. Substantial amendments will require review by the NHS REC will not be implemented until the NHS REC grants favourable opinion.

Public and patient involvement

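### Free-living activity is framed as a pre-to-post outcome but examined across six wears, and the only named test compares two occasions within one arm and not the arms

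*Protocol*

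**What the plan says.** Four parts of the protocol bear on this measure.

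- **Background and Summary.** The protocol says that "this study will enable preliminary assessment of changes (pre-intervention to post-intervention) to a wide range of health outcomes", and free-living activity is among the outcomes listed in that sentence.
- **Aims and outcomes, secondary objective.** Under the line "Outcome measures, collected pre- and post-trial period" the list includes "Free-living physical activity levels via wearable technology", with five example summaries: duration, intensity, frequency, energy expenditure and sedentary time.
- **Free living measures and the trial flow chart.** "Participants will be given a GENEActiv physical activity monitor at six measurement points throughout the study": before the trial period, in weeks 2, 6, 10 and 14, and after it. The stated use is: "Data from complete days (>80% wear time) will be reported to examine any change in physical activity level between measurement points". The flow chart places physical activity level at these six times under "Control measures".
- **Statistical analysis plan section.** For secondary data, "longitudinal differences and interaction effects will be identified using repeated-measures T-tests". Descriptive statistics and multiple imputation are also planned. No significance level and no adjustment for multiple tests is given.

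**The concern.** The measure has two roles. As a secondary outcome, it should show whether training changes habitual activity. As a control measure, it should show what happened to activity during the trial, including whether controls stayed inactive; the control-arm section names contamination as a concern. The protocol does not say which comparison serves which role.

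The named test suits neither role well. A repeated-measures t-test takes two occasions from one group. It cannot treat six occasions together, and it does not estimate the difference between arms, which is what a randomised comparison needs. The interaction effects mentioned in the same sentence require an arm-by-occasion term or, for two occasions, a comparison of change scores between arms.

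The choice of occasions also affects what is measured. The monitor is worn continuously and no rule removes prescribed sessions, so an exercise-arm wear in weeks 2 to 14 can record the intervention itself. A rise from baseline to week 10 could then sit beside no change from pre to post, and the two answer different questions. At stake is a misread secondary or control result, such as apparent contamination of controls where there is none.

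**Working it through.** The protocol gives no error rate or power for this measure, so there is no figure to reproduce. The check has two parts.

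**1. Prescribed exercise inside the in-trial wears**

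Inputs: two observed bike sessions a week, each with three 8-minute work phases (Table 3), and one 45-minute walk a week (unsupervised walking component).

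2 × 3 × 8 + 45 = 48 + 45 = 93 minutes a week.

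Against the lower bound of 150 moderate-intensity minutes in the inactivity criterion: 93 / 150 = 62%.

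This is what is prescribed, not what a wrist monitor will record; cycling in particular may be only partly registered. To the extent that it is recorded, it enters the week 2, 6, 10 and 14 wears of the exercise arm. The pre-trial wear precedes training and the final wear is meant to follow it.

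**2. Chance of a false change under different readings**

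Inputs:
- Occasions: 6. Pairs per arm: 6 × 5 / 2 = 15. Contrasts against baseline: 5. Pre-to-post: 1.
- Size: "The aim is to recruit 40 participants", 20 per arm. With the stated 20% dropout, 20 × 0.80 = 16 per arm. Both sizes were run.
- Assumptions not in the protocol: two-sided 0.05 per test, no adjustment, no true change, normal data.

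If the tests were independent, the chance of at least one false change would be 1 − 0.95^k: 0.537 for k = 15 and 0.226 for k = 5. Tests on the same people are correlated, so the rate was simulated with 40,000 null data sets per setting. The correlation between occasions was either equal for all pairs (its value then cancels out of the differences) or serial, at 0.8 or 0.5 per four weeks.

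| n per arm | Correlation | 15 pairs | 5 against baseline | Pre-to-post |
|---|---|---|---|---|
| 16 | equal | 0.390 | 0.186 | 0.050 |
| 16 | serial 0.8 | 0.334 | 0.163 | 0.049 |
| 16 | serial 0.5 | 0.358 | 0.175 | 0.050 |
| 20 | equal | 0.384 | 0.189 | 0.051 |
| 20 | serial 0.8 | 0.333 | 0.161 | 0.048 |
| 20 | serial 0.5 | 0.357 | 0.177 | 0.051 |

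For a false change in either arm, the rate is 1 − (1 − p)²:
- 15 pairs: 1 − (1 − 0.333)² = 0.555 to 1 − (1 − 0.390)² = 0.628.
- 5 against baseline: 1 − (1 − 0.161)² = 0.296 to 1 − (1 − 0.189)² = 0.342.
- Pre-to-post: 1 − (1 − 0.05)² = 0.0975, about 0.10.

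These rates are for one activity variable. Testing several of the five listed would raise them.

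**The case against.** The strongest reply is that a contrast is already named. The Background and the secondary outcome list both point to pre-to-post for free-living activity, and on that reading the false-change rate is 5% per arm. The in-trial wears can be read as monitoring, consistent with their place under control measures. The sentence on change between measurement points says the data are reported and names no test; similar wording is used for diet, so it may be only a statement of purpose. No stopping rule, judgement of contamination or other decision rests on an activity result, and secondary data serve mainly to plan a later trial. Handling of intermediate wears and multiplicity is commonly left to a separate statistical analysis plan.

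Most of this stands. A reader might infer that the protocol names no contrast, or that false activity changes will often be declared. The documents support neither: pre-to-post is named twice, and nothing commits the investigators to testing every pair or to an unadjusted 0.05.

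Two things remain. The six-wear wording is wider than the pre-to-post wording, and nothing says which governs. And the method is not simply left open: the protocol's own statistical section names a test, and that test does not compare the arms. The second weakness applies to other secondary outcomes too, but it matters more here because there are six occasions and two roles.

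**Conclusion.** The point holds in a limited form. The protocol frames free-living activity as pre-to-post, collects and examines it over six occasions, gives it a second role as a control measure, and offers only a within-arm, two-occasion test. The passages should be reconciled and the test replaced for this measure.

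The size depends on how the plan is read. Under pre-to-post, the error is 5% per arm and about 10% for either arm. Only if every pair were tested unadjusted at two-sided 0.05 would it reach 33–39% per arm and 56–63% for either arm; five contrasts against baseline give 16–19% and 30–34%. The significance level and the all-pairs reading are assumptions. The overlap between in-trial wears and prescribed sessions is separate from these null rates: it concerns what a contrast means, and its extent depends on how much of the prescribed exercise the monitor registers.

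This is a secondary and control measure in a pilot with descriptive primary outcomes, so the consequence is a poorly supported secondary statement, not a threat to the trial's main conclusions.

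**What to change.** In the free living measures section and the statistical analysis plan section, state that the free-living activity outcome is the between-arm difference in change from the pre-trial wear to the post-trial wear, adjusted for the pre-trial value. This makes one comparison per variable and uses the randomisation.

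Analyse the week 2, 6, 10 and 14 wears in one linear mixed model with arm, occasion, an arm-by-occasion term and the pre-trial value as covariate. Report the estimates with confidence intervals as a description of activity during the trial, including possible contamination of controls, in place of separate paired t-tests. Note that exercise-arm values in those weeks may include prescribed sessions.

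Naming one activity variable in advance would limit the number of comparisons further, but which one, and whether to do so, is a matter of preference.

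The cost is a few sentences and slightly more analysis work. No new data are needed.

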A functional fitness test battery has been validated in older adults to assess aspects of fitness that closely relate to the performance of activities of daily living (Rikli and Jones, 1999).

Balance: 8ft up-and-go test performance will be reported as the time (s) taken to get up from a sitting position (on a chair with a straight back and no arms), walk 8ft (2.44m) and return to a sitting position.

Strength: Upper-body strength will be reported as the average of three repetitions of a maximal grip strength test (kg) on each hand. Performance in a 30s chair stand test will be reported as the time (s) to complete five repetitions (strength) and the total number of repetitions completed (strength endurance) from a chair with a straight back and no arms.

Flexibility: Upper-body flexibility will be reported for left and right arms as the average distance (cm) between extended middle fingers in a back scratch test performed three times. Lower-body flexibility will be reported for left and right legs as the average distance (cm) between extended middle finger and the tip of the same-side toes in a chair sit-and-reach test performed three times.

Cardiorespiratory fitness

Participants in both groups will undergo a baseline lactate threshold test to determine the lactate threshold that will inform the exercise training intervention, and measure the cardiorespiratory fitness level of participants.

Lactate threshold test: Lactate threshold will be determined using a submaximal exercise test to an RPE <17 or 80% predicted HRmax on a Lode cycle ergometer. The test will consist of 3 minutes of rest followed by 3 minutes of unloaded (0W) cycling followed by an incremental phase of exercise with an increase in work load (Watts) of between 5 and 25 watts every 3 minutes (Ats and Accp, 2003). The increment will be adjusted based on age, physical activity level and gender, to achieve the desired RPE or HR within 5-10 stages. A rating of perceived exertion (RPE) and blood lactate, measured using an ear lobe capillary blood sample, will be recorded at the end of each stage. Breath-by-breath gas exchange, heart rate, ECG, blood pressure and blood oxygen saturation will be monitored continuously. The test will be terminated if the participant fails to conform to the exercise test protocol, experiences adverse signs or symptoms, requests to stop, or experiences an emergency situation.

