Lactate threshold will be determined by plotting a graph of power in watts (x-axis) against the blood lactate in mM (y-axis). The definition of the blood lactate threshold as the break-point where a curvilinear rise in lactate concentrations is observed when plotted against power will then be used to determine the power at which the lactate threshold occurred. Work rates corresponding to -5%, +5% and +15% of the lactate threshold will be calculated from the lactate – to – work rate relationship. These work rates will then be used as the exercise intensities during the training intervention.

Health and safety: Participants unable to comply with the exercise test, for example due to a health problem raised during the exercise test (e.g. abnormal blood pressure response) or serious discomfort exercising, will discontinue involvement in the study on safety grounds. Abnormal test results will be referred to a cardiologist who will provide follow-up care and advice on the participants continued involvement in the trial. The decision on whether to repeat baseline measures will be discussed with the trial management group; e.g. if follow-up care results in a considerable delay, there may be a need to repeat baseline measures prior to commencing further trial activities.

Randomisation

Eligible, consenting participants will be randomly allocated (1:1) to an exercise training intervention (ETI) or standard care control (CON) group. Randomisation will be performed using a web-based platform.

Trial period measurements

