Participants in the exercise training intervention group will complete a Session Record Card in each observed exercise session. Unsupervised exercise will be monitored using a Home Exercise Diary which will be reviewed each week. Participants will also be provided with a Polar A370 fitness monitor for the duration of the trial period to record all training sessions. Participants will not be required to wear this monitor for the duration of the trial, they will only be required to wear the monitor during the observed and the unsupervised sessions. The Polar A370 fitness monitor is a wrist worn device that measures heart rate continuously using Polar's proprietary 2-LED optical heart rate solution. Participants will be provided with instructions on how to use the Polar A370, participants will be asked to press a button on the face of the fitness monitor, at the start of each observed training sessions. Data from the monitor will be uploaded by the participant once a week. The Polar A370 fitness monitor will be loaned to the participant for the duration of the trial only. The devices are covered by the University of Bath insurance policy.

The primary outcome of acceptability refers to the overall viability of the exercise intervention (e.g. how well can we recruit, can we keep participants engaged, are participants able to achieve the exercise intensities required) and the safety (e.g. do adverse events occur and are they unexpected and related to the trial treatment):

Uptake: Proportion of people approached who attend screening (recruitment rate) and the proportion of people who attend screening that are deemed eligible (screen-pass rate). Demographic characteristics will be compared across those who a recruited and those who decline to participate.

Adherence: Number of observed and unsupervised exercise sessions completed, measured using a Session Record Card, Home Exercise Diary and fitness monitor.

Compliance: Prescribed vs. actual aerobic exercise completed in each observed session will be measured using the fitness monitor. Compliance to unsupervised aerobic exercise will be measured using the fitness monitor.

Retention: Proportion of participants who complete baseline measures (i.e. Visit 2) that also complete follow-up measures (i.e. Visit 3).

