The exercise program is designed to elicit all purported anti-tumour mechanisms of exercise via incorporation of regular vigorous intensity exercise, resistance exercises, as well as longerduration lower intensity exercise. To ensure safety, promote adherence and gains in physical exercise capacity, participants randomised to the exercise intervention will receive a personalised incremental exercise programme based on an initial lactate threshold test, that will generate workload zones (including a target wattage, heart rate and RPE) to ensure participants exercise at predefined intensities throughout the intervention, monitored via fitness monitors that measure continuous heart rate. The programme will be delivered as two home-based, static bike exercise sessions observed by a member of the Research Team via the Microsoft Teams video communication platform and one unsupervised walking exercise session, each week for 16 weeks. At the beginning of each week, during the trial period, participants will be emailed a link to the Microsoft Teams video communication platform. This link will enable participants to attend the training sessions observed by a member of the Research team. Each training session will have a small number of participants, all participants will be given the choice of whether they would like to see other members of the class on the screen at the same time, or not.

Aerobic exercise, beginning at a moderate intensity, (defined as -5% of participants lactate threshold, a rating of perceived exertion of 12-13 and a heart rate of 40-50% of participants VO_{2MAX}) and progressing to vigorous intensity (defined as +15% of participants lactate threshold, a rating of perceived exertion of 15-16 and a heart rate of 70-80% of participants VO_{2MAX}) during observed sessions, is the main component of the exercise programme because it elicits numerous physiological effects that have been hypothetically linked to reduced neoplastic growth (e.g., immune and metabolic changes, and adipose tissue reduction).

Progressive resistance exercise is incorporated into the observed exercise sessions in this study to; (i) to support safe progression through the incremental aerobic exercise programme, (ii) to add variety to the exercise sessions to maintain participant enjoyment and motivation to continue, (iii) for diverse outcomes for older adults, e.g. reduce falls risk (Buchner et al., 1997).

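### Observed-session compliance, a primary outcome, is defined by a heart-rate monitor although intervals are prescribed and recorded in watts; the linked %VO2max bands cannot all match those watts if oxygen uptake is linear

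*Protocol*

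**What the plan says.** The primary outcome list (Protocol, Aims and outcomes) includes compliance, a comparison of the aerobic exercise prescribed with that performed. The section Trial period measurements gives the instrument: "Prescribed vs. actual aerobic exercise completed in each observed session will be measured using the fitness monitor". It names no second source, whereas the adherence definition just before it names three. The same section describes the monitor as a wrist-worn optical heart-rate device. It also explains what the acceptability outcome is for, asking among other things: "are participants able to achieve the exercise intensities required".

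The prescription is in watts. The lactate threshold test yields work rates below, at and above threshold, and the protocol states: "These work rates will then be used as the exercise intensities during the training intervention". Exercise sessions (Aerobic component) gives each participant a target zone in watts, and Table 3 sets the steps at -5%, 0, +5% and +15% of threshold watts. The text beside Table 3 has power, heart rate and RPE noted for each interval.

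Heart rate is a target too. The arm description says the threshold test will "generate workload zones (including a target wattage, heart rate and RPE) to ensure participants exercise at predefined intensities throughout the intervention", and that these are "monitored via fitness monitors that measure continuous heart rate". It then expresses the heart-rate target through %VO2max. Vigorous intensity, for example, is "defined as +15% of participants lactate threshold, a rating of perceived exertion of 15-16 and a heart rate of 70-80% of participants" VO2max. Table 3 carries the same bands.

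**The concern.** The main quantity prescribed for the intervals is power, and both the target and the achieved value are available, yet the definition of the primary outcome uses neither. It relies on heart rate, whose printed target comes through a %VO2max band. The only exercise test described is a "submaximal exercise test to an RPE <17 or 80% predicted HRmax on a Lode cycle ergometer", so the VO2max behind those bands would have to be predicted, while threshold watts are read from the test directly.

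If the bands and the watts in Table 3 disagree, a participant can meet one target only by missing the other. Compliance is to be reported as a proportion (Protocol, Statistical analysis plan). A low figure could then reflect the table and not what participants did, and it could mislead the design of the future trial that this pilot is meant to inform.

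**Working it through.** **Inputs from Table 3.** The threshold percentages are taken as fractions of threshold watts, as the column heading and the Aerobic component text indicate.

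| Weeks | Watts, as a multiple k of threshold watts | %VO2max band |
|---|---|---|
| 1-2 | 0.95 | 40-50 |
| 3-6 | 1.00 | 50-60 |
| 7-10 | 1.05 | 60-70 |
| 11-16 | 1.15 | 70-80 |

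The session length in the table reproduces: 3 x (8 + 2) = 30 minutes. The pairing of watts with bands does not, as follows.

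**Assumption.** The protocol gives no relation between uptake and watts. Assume %VO2max = c + s x k, a straight line with c ≥ 0 (uptake at zero watts cannot be negative).

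**Ratio check.** With c ≥ 0, the ratio of uptake between two rows cannot exceed the ratio of their watts.
- Weeks 1-2 to 11-16: watts 1.15/0.95 = 1.21. The bands need at least 70/50 = 1.40.
- Weeks 1-2 to 7-10: watts 1.05/0.95 = 1.105. The bands need at least 60/50 = 1.20.
- Weeks 3-6 to 11-16: watts 1.15/1.00 = 1.15. The bands need at least 70/60 = 1.167.

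So no two non-adjacent rows can agree. Any three of the four rows contain such a pair, so no three can agree either. Adjacent pairs can.

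**How far apart.** Put weeks 1-2 at the top of their band (50% at k = 0.95), the most favourable start, so that s = (50 - c)/0.95:

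| Intercept c (% of VO2max, assumed) | k = 0.95 | 1.00 | 1.05 | 1.15 |
|---|---|---|---|---|
| 0 | 50.0 | 52.6 | 55.3 | 60.5 |
| 10 | 50.0 | 52.1 | 54.2 | 58.4 |
| 20 | 50.0 | 51.6 | 53.2 | 56.3 |
| Printed band | 40-50 | 50-60 | 60-70 | 70-80 |

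A higher intercept makes the mismatch larger.

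**What would make all four rows fit.** At most 50 at k = 0.95 and at least 60 at k = 1.05 require s ≥ 10/0.10 = 100. Then c ≤ 50 - 0.95 x 100 = -45. A straight line through all four bands therefore needs an intercept of -45% of VO2max or lower, which is physically impossible.

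**Departure from linearity.** If uptake rises more steeply above threshold, the gap narrows. From the c = 0 row, the excess needed to reach the lower band edges is 60 - 55.3 = 4.7 points at +5% and 70 - 60.5 = 9.5 points at +15%. The documents do not say whether such an excess is to be expected.

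**The case against.** Three points on the other side have force.

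First, the compliance sentence names the monitor but does not exclude other records. Power is noted for each interval and nothing stops the team from reporting it. A reader might infer that the protocol rules power out, or that the data needed will be lost. Neither follows: watts, heart rate and RPE are all collected.

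Second, heart rate is one of the stated targets, it is captured by a device and uploaded weekly, and the same device covers the walks. A reader might infer that the monitor measures the wrong thing. It does not; it measures one prescribed dimension and leaves out the one in which the intervals are set.

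Third, a reader might infer that participants on the prescribed watts will be scored as non-compliant. The protocol states no such rule. The heart-rate target is said to come from the threshold test, during which "Breath-by-breath gas exchange, heart rate, ECG, blood pressure and blood oxygen saturation will be monitored continuously", so it could be read at the prescribed watts. On that reading the %VO2max bands never enter the score. Scoring rules and tolerances may also sit in a statistical analysis plan that is not at hand, and their absence is no fault.

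What remains is that the definition itself names only the heart-rate device, and that the printed bands and watts disagree under the linear assumption. The first of these does not depend on any physiological assumption.

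**Conclusion.** The point holds in a limited form, as a cheap improvement. As written, the primary-outcome definition for observed sessions leaves out the recorded power, which is the direct measure of whether the prescribed intensity was reached. Separately, the watt and %VO2max columns of Table 3 cannot all be met together if uptake is linear in watts with a non-negative intercept: a 21% rise against at least 40%.

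The two problems meet only if compliance is judged on the bands, which the protocol neither states nor excludes. A steeper rise in uptake above threshold would reduce the conflict. The protocol sets no pass mark on compliance, and no sample size or randomised comparison depends on it. The harm is to the interpretation of one primary outcome and not to the data.

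**What to change.** 1. In the compliance definition, add recorded interval power as a percentage of target watts for the observed sessions. Report it as a continuous percentage for each of the four phases of Table 3.
2. If a within-target share is also wanted, have the exercise lead set the tolerance in advance. A tolerance alone can hide non-progression. A participant who stays at the weeks 1-2 watts reaches 100%, 0.95/1.00 = 95.0%, 0.95/1.05 = 90.5% and 0.95/1.15 = 82.6% of target in the four phases. A margin of 10% either way would pass all of weeks 1-10 and flag only weeks 11-16. Percentages by phase show the drift.
3. Keep monitor heart rate, RPE and duration as supporting measures, and keep the monitor for the walks.
4. Derive each participant's heart-rate targets at the prescribed watts from their own threshold test. Correct or drop the %VO2max column of Table 3 and the matching text in the arm description.

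The cost is one reworded outcome definition, one table column and the matching sentence, with no new measurement. The downside is that power from the home bike may be less exact than from the laboratory ergometer, which is a reason to keep the supporting measures and to choose any tolerance realistically.
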